	S		Cy	cle 0			Сус	le 1		C: onw		ontinuec atment)	(# 0		follow after la	v-up ast dose)	val ntil 2W)	
Cycle Day	-21 to -1	Day 1	Day 7	Day 15	Day 22	Day 1	Day 8	Day 15	Day 22	Day 1	Day 8	Study Treatment Discontinued (last dose of study treatment)	30 days	60 days	90 days	180 days (6 months)	Progression/Survival Follow-up (Q8W until 8 months, then Q12W)	
Visit window (± days)	-	-	-	-	± 1	± 3	-	± 1		± 3	± 1	Study T	± 3	± 7	± 7	± 7	Pro Foll	
Dosing with ceralasertib (self-administered) w		`	Days o 7)			X (Day s 1 to 7 of ever y cycle)				X (Day s 1 to 7 of ever y cycle)								Sections 6.2.2.2 and 6.4
Dosing with durvalumab (IV infusion) w							X				X							Sections 6.2.1.2 and 6.2.1.3
Dosing diary y, z			JI.	J	X (Da	nys 1 to 7	of ever	y cycle)										Section 6.4
Survival status ^{aa}													X	X	X	X	X	Sections 7.1.3 and 8.1.2
Subsequent anticancer therapy bb												X	X	X	X	X	X	Section 7.1.2

[figure not shown]
If screening assessments have been performed within 3 days prior to starting study intervention, they do not have to be repeated at Cycle 1 Day 1 if the patient's condition has not changed.

- Written informed consent and any locally required privacy act document authorisation must be obtained prior to performing any protocol-specific procedures, including screening/baseline evaluations.
- Submission of archival tumour tissue is mandatory for all patients. A minimum of 20 freshly cut unstained sections from the archival tumour block are accepted if tumour blocks cannot be submitted, however tumour tissue blocks are preferred.
- All study patients in the biopsy substudy are required to provide 3 mandatory fresh tumour biopsy samples for testing at Screening (Days -21 to -1), on-ceralasertib treatment, Cycle 0 (on Day 7) of ceralasertib monotherapy, and off-ceralasertib treatment, Cycle 0 (between Days 15 to 28). For sample collection details refer to Section 8.6 of the protocol.
- Submission of the cytological or histological report, and molecular report confirming BRAF mutation status is mandatory at screening. In addition, the investigator must confirm the type of PD-(L)1 resistance at screening and whether the LDH is normal or above upper limit of normal, in order to stratify the patients accordingly. Other genomic characteristics will be collected where known eg, NRAS, c-kit, PD-(L)1, NF1, MSI.

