- Patients who develop a ≥ Grade 3 of anaemia, neutropenia, or thrombocytopenia during the treatment period will also need to have additional assessments also on Day 15 until there is no evidence of ≥ Grade 3 anaemia, neutropenia, or thrombocytopenia for at least 2 cycles.
- ⁿ Coagulation will be performed at screening and as clinically indicated during subsequent visits.
- Women of childbearing potential only. Serum pregnancy test at screening, urine test at other time points up to 90 days after the last dose of study treatment. For country-specific requirements for Belgium and France see Appendices K 1.1 and K 1.2, respectively.

- CT scans of the chest, abdomen, and pelvis (or MRI where CT is contraindicated) should be conducted every 8 weeks (±1 week) after the start of study treatment (Cycle 1 Day 1) up to 18 months, then every 12 weeks (±1 week) until objective disease progression as per RECIST 1.1, irrespective of treatment decisions. In the event of study treatment interruptions or delays, tumour assessments should proceed to schedule relative to Cycle 1 Day 1. Soft tissue or visceral progression observed by CT or MRI, according to RECIST 1.1, does not require a confirmatory scan. To confirm progression based on non-target lesions, additional scans or images / photographs may be required for submission for BICR.
- ^q Baseline contrast enhanced MRI brain scan assessment (or CT if MRI is contraindicated) for all patients at screening.

r	CCI	
S	CCI	
t	CCI	

- For ceralasertib, PK sample will be collected in all patients at pre-dose (up to 1 hour prior) and 1 hour (± 30 min) post-dose on Day 1 and Day 7 of Cycle 0. For durvalumab, PK sample will be collected in all patients at study treatment discontinuation and at 90 days after last dose of the study treatment. For non-dosing days, PK sample will be collected at similar times as dosing day.
- Immunogenicity sample for durvalumab to be collected at screening, end of treatment, 90 days and 6 months (± 7 days) after last dose.
- W Ceralasertib administered twice daily from Days 1 to 7 at Cycle 0 (a 28-day cycle) and at each cycle, Cycle 1 onwards. Durvalumab administered on Day 8 of each cycle, from Cycle 1 onwards.
- Cycle 1 may start after the off-treatment biopsy is collected ie, between Cycle 0, Days 15 to 28, and if blood parameters are within limits. For country-specific requirements for Belgium see Appendix K 1.1.

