Biopsy sub-study: An open-label, non-randomised, biopsy sub-study is planned in patients suitable for 3 mandatory biopsies. Patients recruited into the biopsy sub-study will receive 1 cycle of ceralasertib monotherapy (Cycle 0) followed by ceralasertib plus durvalumab from Cycle 1.

The biopsy sub-study is anticipated to recruit patients from pre-defined/selected subset of sites and the estimated number of patients in the biopsy sub-study is as follows:

Enrolled	Estimated patients
Evaluable tumour biopsy patients	Estimated 30 patients

Note: "Enrolled" means a patient's, or their legally acceptable representative's, agreement to participate in a clinical study following completion of the informed consent process. Potential patients who are screened for the purpose of determining eligibility for the study, but are not randomised/assigned in the study, are considered "screen failures", unless otherwise specified by the protocol. For country-specific requirements for Germany see Appendix K 1.3.

Serial tumour biopsies are mandated in the patients recruited into the biopsy sub-study and will be taken at baseline during the screening period, during treatment with ceralasertib monotherapy and during the off-treatment period of ceralasertib monotherapy.

During the Cycle 0 treatment period, patients will be treated with ceralasertib 240 mg BD Days 1 to 7, followed by an off-treatment period between Days 8 to 28. From Cycle 1 onwards, patients will be treated with the combination of ceralasertib 240 mg BD Days 1 to 7 plus durvalumab 1500 mg Day 8, Q28D, until progressive disease, unacceptable toxicity, withdrawal of consent, or if a study treatment discontinuation criterion is met.

For dose modification recommendation, stopping rules and discontinuation for ceralasertib monotherapy or in combination with durvalumab, please refer guidance for the main study (Section 6.6).

4.1.1 Study Conduct Mitigation During Study Disruptions Due to Cases of Civil Crisis, Natural Disaster, or Public Health Crisis

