6.2.2.2 Ceralasertib Administration

Ceralasertib tablets should be taken with a glass of water. When ceralasertib is administered, patients must fast (water permitted) for at least 2 hours prior to taking a dose, to at least 1 hour post-dose for all doses.

Ceralasertib will be administered orally 240 mg twice daily, approximately 12 ± 2 hours apart, starting on Day 1 until Day 7, in each treatment cycle of both the treatment arms in the main study. In the biopsy sub-study, patients will self-administer ceralasertib tablets from Day 1 until Day 7 of Cycle 0, followed by no study treatment between Day 8 and Day 28, and from Day 1 until Day 7 Cycle 1 onwards.

Patients must receive ceralasertib for 7 days within each 28-day cycle. A cycle must not be < 28 days. Ceralasertib must not be given on any other days of the cycle, and dosing days must stay relative to Day 1 of each cycle. In case of drug interruption within the planned Days 1 to 7 dosing window (for any reason), resumption of treatment can only take place within the planned dosing window and not beyond, even if this means the patient receives less than the specified 7 days of ceralasertib dosing in the particular cycle. Dosing after Cycle Day 7 is not permitted and the planned 21 days off treatment should not be reduced.

Patients are allowed to take the scheduled dose up to 2 hours after the scheduled dose time. If the interval between two doses is more than 14 hours, then the missed dose should not be taken and the patient should continue with the next dose at the allotted time. If the patient wishes to bring forward the time of their scheduled dose, the dose can be taken up to a maximum of 2 hours prior to the scheduled time, ie, \pm 2-hour window.

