o Women of childbearing potential only. Serum pregnancy test at screening, urine test at other time points up to 6 months after the last dose of study treatment. A urine pregnancy test must be locally performed for WOCBP 6 months after last dose of study treatment. If the pregnancy test is positive, the investigator must report it per procedures outlined in Section 8.3.13.

Revised table

Procedure	Screening a		Intervention period (28-day cycles)											erventio	on follov	w-up perio	od	Details in CSP section or appendix
	Scr	Cycle 0				Cycle 1				C2- onwards		Safety follow-up (# of days after last dose) (# of was after last dose) (# of was after last dose) (# of was after last dose)						
Cycle Day	-21 to -1	Day 1	Day 7	Day 15	Day 22	Day 1	Day 8	Day 15	Day 22	Day 1	Day 8	ıtment of stud	30 days	30 days 60 days 90 days 6 months			ession/Surviv -up (Q8W un ths, then O12	
Visit window (± days)	1	-	-	-	±1	± 3	-	± 1		± 3	± 1	Study Trea (last dose	±3	± 7	± 7	+ 7	Progre Follow	
Pregnancy test (WOCBP only)°	X	X	X X				X			X	X	X	X		Section 8.2.5			

Revised text

o Women of childbearing potential only. Serum pregnancy test at screening, urine test at other time points up to 6 months after the last dose of study treatment.

Revised text

x Cycle 1 may start after the off-treatment biopsy is collected ie, between Cycle 0, Days 22 to 28, and if blood parameters are within limits.

Section 5.1 (Inclusion Criteria)

Inclusion criterion 16

Revised text

- 16 Contraceptive use by men or women should be consistent with local regulations regarding the methods of contraception for those participating in clinical studies (Section 5.3.1)
 - (a) Male patients: Male patients who intend to be sexually active with a female partner of childbearing potential must be surgically sterile or using an acceptable method of contraception (see Section 5.3.1) from the time of screening throughout the total duration of the study and 6 months after the last dose of the study treatment, (ceralasertib monotherapy and ceralasertib in combination with durvalumab), in order to prevent pregnancy in a partner. Male patients must not donate or bank sperm during this same time period.
 - (b) Female patients:
 - (i) Negative pregnancy test (serum) for women of childbearing potential.

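### Table 3 lets biopsy sub-study Cycle 1 start on Cycle 0 Days 15–28 (Belgium: Days 22–28), and every one of those days breaks the dosing rule in Section 6.2.2.2

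*Protocol*

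**What the plan says.** The Table 3 footnote (Protocol, Section 1.3) on the start of Cycle 1, the first combination cycle, says that it "may start after the off-treatment biopsy is collected ie, between Cycle 0, Days 15 to 28, and if blood parameters are within limits". The Belgian text in Appendix K 1.1 replaces the range: "between Cycle 0, Days 22 to 28, and if blood parameters are within limits".

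Section 6.2.2.2 gives the dosing rule. In general terms, "A cycle must not be < 28 days" and "the planned 21 days off treatment should not be reduced". For the biopsy sub-study it describes ceralasertib on Days 1 to 7 of Cycle 0, "followed by no study treatment between Day 8 and Day 28".

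Three other places agree with Section 6.2.2.2. Sections 1.1 and 4.1 both describe Cycle 0 dosing as "followed by an off-treatment period between Days 8 to 28". Footnote w of Table 3, next to the footnote at issue, calls Cycle 0 a 28-day cycle.

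**The concern.** Cycle 1 Day 1 is a ceralasertib dosing day, so permission to start Cycle 1 is permission to restart the drug. The footnote gives that permission inside the period that Section 6.2.2.2 keeps free of study treatment.

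Two things are at stake. The first is compliance. Section 8 requires adherence to both the design requirements and the Schedule of Activities, and allows no waivers. A patient who started Cycle 1 on, say, Day 18 followed the schedule and broke the dosing section, so the start cannot be clearly classed as compliant or as a deviation.

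The second is how sub-study safety is read. Anaemia, neutropenia and thrombocytopenia are identified risks of ceralasertib, and Section 4.3 supports the 7-day schedule partly by longer time off drug and less haematological toxicity. If some patients entered the first combination cycle after 7 days off and others after 21, the safety summary mixes different exposures.

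**Working it through.** Inputs: ceralasertib on Cycle 0 Days 1–7; minimum cycle 28 days and 21 days off (Section 6.2.2.2); permitted start days 15–28 (Table 3 footnote) and 22–28 (Appendix K 1.1); at least two weeks off for platelet and neutrophil recovery (Section 4.3.1); a visit window of ±3 days for Cycle 1 Day 1 (Table 3).

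The plan's own figure first: 28 − 7 = 21 days off, which agrees with Section 6.2.2.2.

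For a Cycle 1 start on Cycle 0 Day d, with the last Cycle 0 dose on Day 7:

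- cycle length = d − 1
- days off = (d − 1) − 7 = d − 8

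Both limits give the same earliest day: d − 1 ≥ 28 gives d ≥ 29, and d − 8 ≥ 21 gives d ≥ 29.

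| Start day d | Cycle length (d − 1) | Days off (d − 8) | Meets Section 6.2.2.2? |
|---|---|---|---|
| 15 | 14 | 7 | no |
| 21 | 20 | 13 | no |
| 22 | 21 | 14 | no |
| 26 | 25 | 18 | no |
| 28 | 27 | 20 | no |
| 29 | 28 | 21 | yes |

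Counts of permitted start days:

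- Global footnote: 28 − 15 + 1 = 14 days. The longest cycle among them is 27 days, so all 14 break the rule.
- Belgian footnote: 28 − 22 + 1 = 7 days. All 7 break the rule.
- Fewer than 14 days off means d − 8 < 14, so d < 22. That is Days 15–21 in the global text (7 start days, 7 to 13 days off) and none in the Belgian text.
- Visit window: 29 − 3 = 26, so Days 26–28 lie inside it. The Protocol does not say whether the window may shorten a cycle.

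Primary sub-study endpoint: the biopsies for CD8+ infiltration are taken at screening, on Cycle 0 Day 7 and between Days 15 and 28. Cycle 1 may follow only after the last of these, so the start day cannot alter the measurements.

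**The case against.** The strongest reply is that no site is forced into a breach. The footnote says only that Cycle 1 may start. A site that waits until Day 29 obeys every text. The dosing row of Table 3 also refers to Section 6.2.2.2, whose wording on cycle length is mandatory. This stands as far as it goes, but a permission that the governing section forbids on every day it names is still wrong as written.

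A second reply is that Days 15 to 28 only repeats the biopsy window. That does not remove the conflict, because Cycle 1 could still follow directly after a Day 15 biopsy. Belgium also changed this range and shows no change to the biopsy timing, which suggests a start window and perhaps a deliberate flexibility. For that reason the fix below offers two routes.

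A third is that Section 6.6 lets dosing intervals be shortened. That text concerns realigning later cycles after durvalumab delays, and Cycle 0 contains no durvalumab.

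Stronger conclusions are tempting, but the Protocol does not support them:

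- A reader might infer that early starters were dosed before their marrow recovered. Section 4.3.1 does not tie the two-week figure to a single 7-day course, and the same model shows less haematological toxicity with 7 days than with 14. The footnote also requires blood parameters within limits, Table 3 has laboratory tests on Cycle 0 Days 15 and 22, and a blood count taken on a dosing day is to be checked before dosing.
- A reader might measure the problem by the 11 of 14 days (Belgium: 4 of 7) that fall outside the ±3-day window. That count adds nothing, since all 14 and all 7 already break the 28-day minimum. These are calendar days, not patients.
- A reader might expect the correction to change how patients are treated. The summary of changes says that the study is no longer recruiting, and Cycle 0 happens once, at entry.

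**Conclusion.** The inconsistency is real and minor. The Table 3 footnote is wrong as written: all 14 start days it names, and all 7 in the Belgian version, conflict with Section 6.2.2.2, Sections 1.1 and 4.1 and footnote w. The largest departure is a Day 15 start, with a 14-day cycle instead of 28 and 7 days off instead of 21.

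This rests on reading the footnote as permission to start Cycle 1 within the stated days, or directly after a biopsy taken within them; the day counts follow from either. How many patients started early is not in the Protocol, and nothing here shows that any patient was harmed. With recruitment closed, the practical effect is to settle whether starts already made were compliant or deviations, and to make the sub-study safety data easier to read.

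**What to change.** Make one rule govern, by either route.

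1. If no early start was intended: change the Table 3 footnote and the Belgian footnote in Appendix K 1.1 so that Cycle 1 starts no earlier than Cycle 0 Day 29, after the off-treatment biopsy and if blood parameters are within limits. It would help to state in Section 6.2.2.2 whether the ±3-day visit window may shorten a cycle, since Days 26–28 otherwise stay open to argument. Cost: two footnotes, and one sentence if the window is clarified.
2. If an early start was intended, as the Belgian text suggests: write an explicit sub-study exception into Section 6.2.2.2 with a floor of Day 22 (22 − 8 = 14 days off), change the Table 3 footnote to Days 22 to 28, and align footnote w and Sections 1.1 and 4.1. Cost: one exception and four matching edits.

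Under either route, say how starts already made under the present footnote are to be classed.

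An optional addition is to derive the actual days off drug before Cycle 1 and show them descriptively beside sub-study haematological toxicity. Section 6.4 already has treatment start and stop dates recorded in the eCRF, so this needs one derived variable and no new data.

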2 INTRODUCTION

2.1 Study Rationale

This Phase 2 study aims to evaluate the efficacy and safety/tolerability of ceralasertib (AZD6738), when administered as monotherapy and in combination with durvalumab in patients with unresectable or advanced melanoma and primary or secondary resistance to PD-(L)1 inhibition. The rationale for conducting the main study is supported by clinical data from ongoing studies, unmet need, and the evidence of ceralasertib modulating the immune environment.

An open-label, non-randomised, biopsy sub-study is also planned in patients suitable for 3 mandatory biopsies. The rationale for conducting the biopsy sub-study is to understand the MoA of ceralasertib plus durvalumab and investigate ceralasertib as an immune modulator.

The background to the study rationale is summarised in Section 2.2 and Section 2.3. The rationale for study design summarised in Section 4.2 and justification for study treatment dose summarised in Section 4.3.

2.2 Background

2.2.1 Immunotherapies

It is increasingly understood that cancers are recognised by the immune system, and under some circumstances, the immune system may control or even eliminate tumours (Dunn et al 2004).

PD-L1 is part of a complex system of receptors and ligands that are involved in controlling T-cell activation. The PD-1 receptor (cluster of differentiation [CD]279) is expressed on the surface of activated T-cells (Keir et al 2008). It has 2 known ligands: PD-L1 (B7-H1; CD274) and programmed death-ligand 2 (PD-L2) (B7-DC; CD273) (Okazaki and Honjo 2007). PD-1 and PD-L1/PD-L2 belong to a family of immune checkpoint proteins that act as co-inhibitory factors, which can halt or limit the development of T-cell response. When PD-L1 binds to PD-1, an inhibitory signal is transmitted into the T-cell, which reduces cytokine production and suppresses T-cell proliferation. Tumour cells exploit this immune checkpoint pathway as a mechanism to evade detection and inhibit immune response.

PD-L1 is constitutively expressed by B-cells, dendritic cells, and macrophages (Qin et al 2016). Importantly, PD-L1 is commonly over-expressed on tumour cells or on non-transformed cells in the tumour microenvironment (Pardoll 2012). PD-L1 expressed on the tumour cells binds to PD-1 receptors on the activated T-cells, leading to the inhibition of cytotoxic T-cells. These deactivated T-cells remain inhibited in the tumour microenvironment.

The PD-1/PD-L1 pathway represents an adaptive immune resistance mechanism that is exerted by tumour cells in response to endogenous antitumour activity.

The inhibitory mechanism described above is co-opted by tumours that express PD-L1 as a way of evading immune detection and elimination. The binding of an anti-PD-L1 agent to the PD-L1 receptor inhibits the interaction of PD-L1 with the PD-1 and CD80 receptors expressed on immune cells. This activity overcomes PD-L1-mediated inhibition of antitumour immunity. While functional blockade of PD-L1 results in T-cell reactivation, this mechanism of action is different from direct agonism of a stimulatory receptor such as CD28.

PD-L1 is expressed in a broad range of cancers. Based on these findings, an anti-PD-L1 antibody could be used therapeutically to enhance antitumour immune responses in participants with cancer. Results of pre-clinical and clinical studies of monoclonal antibodies (mAbs) targeting the PD-L1/PD-1 pathway have shown evidence of clinical activity and a manageable safety profile, supporting the hypothesis that an anti-PD-L1 antibody could be used to therapeutically enhance antitumour immune response in participants with cancer (Brahmer et al 2012, Hirano et al 2005, Iwai et al 2002, Okudaira et al 2009, Topalian et al 2012, Zhang et al 2008) with responses that tend to be more pronounced in participants with tumours that express PD-L1 (Powles et al 2014, Rizvi et al 2015, Segal et al 2015). In addition, high mutational burden (eg, in bladder carcinoma; Alexandrov et al 2013) may contribute to the responses seen with immune therapy.

In contrast, CTLA-4 is constitutively expressed by regulatory T-cells and upregulated on activated T-cells. CTLA-4 delivers a negative regulatory signal to T-cells upon binding of CD80 (B7.1) or CD86 (B7.2) ligands on antigen-presenting cells (Fife and Bluestone 2008). Blockade of CTLA-4 binding to CD80/86 by anti-CTLA-4 antibodies results in markedly enhanced T-cell activation and antitumour activity in animal models, including killing of established murine solid tumours and induction of protective antitumour immunity. Therefore, it is expected that treatment with an anti-CTLA-4 antibody will lead to increased activation of the human immune system, increasing antitumour activity in participants with solid tumours.

Pre-clinical data have now been added to a wealth of clinical data showing that blockade of negative regulatory signals to T-cells such as CTLA-4 and PD-L1 has promising clinical activity. Ipilimumab was first granted United States (US) FDA approval for the treatment of metastatic melanoma and is currently under investigation for several other malignancies. Nivolumab and pembrolizumab, 2 anti-PD-1 agents, and atezolizumab, an anti-PD-L1 agent, have been granted approvals by agencies for the treatment of a number of malignancies including metastatic melanoma, squamous and non-squamous cell non-small-cell lung cancer, squamous cell carcinoma of the head and neck, and urothelial carcinoma. In addition, there are data from agents in the anti-PD-1/PD-L1 class showing clinical activity in a wide range of tumour types.

